### 1.2 Findings from pre-clinical and clinical studies

Currently, there are limited data regarding the early start of anticoagulation therapy following embolic stroke.

In the review of our local stroke database from October 2011 until December 2013, we examined the records of 336 small to medium stroke patients admitted to Tampa General Hospital with an ischemic stroke secondary to atrial fibrillation. The average age in our study population was  $75.3 \pm 1.83$  years of age. Stroke risk was similar to other AF groups in the literature, possessing an average CHADS2 score of  $2.6 \pm 0.26$  on admission; average CHA2DS2-VASc score was  $4.4 \pm 0.4$ . Average hospital stay was  $9.8 \pm 1.49$  days. We observed a  $24.7\% \pm 6.2\%$  mortality rate in our population prior to discharge. In addition, stroke survivors had a 5.1% recurrent non-fatal stroke risk. Patients with disabling or fatal

strokes were of a more advanced age than those who survived without severe disability ( $78.0 \pm 1.96$  years vs  $69.7 \pm 3.50$  years,  $p < 0.001$ ). Our data indicate that the risk of fatal to recurrent stroke is approximately 25 % with standard treatment (initiating anticoagulation approximately seven to fourteen days after signs and symptoms) for this group of patients.

The HAEST trial indicated that low molecular weight heparin results in a reduction in mortality and disability when used early (30 hours post stroke) in the treatment of ischemic stroke; however, this benefit is offset by an increased risk of intracranial hemorrhage

The previous studies on novel anticoagulation (NOAC) excluded subjects with a stroke/TIA within seven or less days; however, these randomized trials consistently demonstrated a lower risk of intracranial bleed compared to traditional anticoagulants ( see table 2).

[figure not shown]
ARISTOTLE followed a limited number of subjects (44) who suffered a stroke/TIA, between 7 and 14 days prior to randomization to treatment with either Apixaban or warfarin. There was only 1 subject in the warfarin group who suffered a major bleed. There were no recurrent stroke or systemic embolism in any of the 44 patients.

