### **4.2.2 Total Number of Study Sites/Total Number of Subjects Projected**

The study will be conducted at University of South Florida (USF Health's South Center for Advanced Health Care, USF Health's Morsani Center for Advance Health Care , Tampa General Hospital), University of Louisville (hospital and clinic), University of California Los Angeles (hospital and clinic), and Bayfront Cardiovascular Sciences for a total of 4 enrolling sites.

Recruitment will stop when approximately 120 subjects meeting eligibility criteria are enrolled. To account for drop-outs as well as screen-failures up to 125 subjects will be consented and randomized.

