#### **8.1.2 Efficacy Analysis/Primary Aim**

For the main outcomes, the proportion of patients with any primary outcome (fatal stroke, recurrent ischemic stroke, transient ischemic attack) will be computed along with the 95% confidence interval for the differences in treatment arms.

The primary outcome is defined as any component of the composite primary outcome occurred within 30 and 180 days or otherwise had adequate follow-up. Logistic regression models will be fitted with the primary outcome as the dependent variable and the SUBGROUP: (1) Apixaban TIA: day 0-3; (2). Apixaban small stroke: day 3-5; (3). Apixaban medium stroke: day 7-9; (4) warfarin TIA: day 7±5; (5) warfarin small stroke: day 14±5; (6) warfarin medium stroke: day 14±5 as the primary independent variable. The overall treatment effect will be assessed by the ESTIMATE and LSMEANS of all the Apixaban groups to all the warfarin groups. Comparison between individual subgroups will be assessed by constructing different ESTIMATE. For example, (1) Apixaban TIA versus (5) warfarin Small stroke: day 14±5. These analyses will be implemented by using SAS 9.2 PROC LOGISTIC which has the ESTIMATE and the LSMEANS statements for the group comparisons. P<0.05 is used for the overall treatment effects. All other subsequent subgroup testing will be adjusted for multiple comparisons by using PROC PLM.

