**8.1.5 Sample Size and Power**

As a pilot, open-label study, this project is intended to generate data to be used in the development of future, larger studies. A total of 120 patients are expected to be available and eligible to participate in this study and up to 125 may be screened in order to yield 120 randomized participants.

Review of our database indicates the risk of fatal or recurrent stroke in patients with atrial fibrillation is approximately 20% with standard treatment . To calculate expected power in this study, this established risk was used as the basis for estimates that could be expected with this treatment if it is successful. Given the parameters of conducting a 2-sided test with alpha = .05, and equal allocation to treatment and control groups (50 patients per group), power calculations were conducted using various ratios of outcomes (i.e. fatal or recurrent stroke) in the control group compared to the experimental group. The following results were obtained:

Power	Detectable outcome Risk in control / Risk in experimental
80% power	2.30

90% power	2.52
99% power	3.00

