### 8.1.6 Randomization

Randomization of treatment was calculated in SAS 9.4 using a stratified, blocked PLAN procedure. For the 120 subjects to be randomized to either apixaban or warfarin, a random seed number was generated. Each subgroup of stroke type (small stroke, medium stroke and TIA) was randomized implementing block randomization using four blocks of 10. The treatment allocation was created by an unblinded statistician and given to the TGH research pharmacy. Blinded study envelopes are provided to study team members for randomization.

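### The power table in section 8.1.5 is wrong for a reduction from a 20% control risk: with 50 per group the three ratios have about 36%, 41% and 50% power, not 80%, 90% and 99%

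*Combined protocol and SAP*

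**What the plan says.** Section 8.1.5 describes the study as a pilot of 120 patients and then gives a power calculation. Its inputs are:

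- Baseline risk: "the risk of fatal or recurrent stroke in patients with atrial fibrillation is approximately 20% with standard treatment", with the added remark that "this established risk was used as the basis for estimates that could be expected with this treatment if it is successful".
- Test and size: two-sided, alpha 0.05, "equal allocation to treatment and control groups (50 patients per group), power calculations were conducted using various ratios of outcomes".
- Effect measure: the table column is headed "Detectable outcome Risk in control / Risk in experimental".
- Results: 2.30 at 80% power, 2.52 at 90% and 3.00 at 99%.

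Two of these inputs differ from other sections. Section 8.1.6 speaks of "For the 120 subjects to be randomized to either apixaban or warfarin", which at 1:1 allocation is 60 per arm, and section 4.2.2 says "To account for drop-outs as well as screen-failures up to 125 subjects will be consented and randomized". Section 1.2 puts the database risk higher: "Our data indicate that the risk of fatal to recurrent stroke is approximately 25 % with standard treatment".

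For the analysis itself, section 8.1.2 plans a logistic regression with an overall treatment contrast tested at P<0.05. It also says that the proportions with an event "will be computed along with the 95% confidence interval for the differences in treatment arms".

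**The concern.** A fall from 20% to 8.7% with 50 patients per group means about 10 events against 4 or 5. A two-sided 5% test cannot have 80% power for that. The ratios look like those for an increase from 20%, where the absolute differences are much larger.

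This is the only power statement in the plan, and section 8.1.5 says the pilot is meant to feed the design of larger studies. If the result is null, a reader would take it that a 2.3-fold reduction had an 80% chance of being found. At the stated 20% control risk the trial would miss such a reduction more often than not. A successor trial planned from the same table would be badly undersized.

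**Working it through.** **Inputs** (all from section 8.1.5 unless noted): control risk 0.20; ratio control/experimental of 2.30, 2.52 and 3.00; n = 50 per group; two-sided alpha 0.05. Sensitivity inputs: n = 60 per group (120 randomised, sections 8.1.5 and 8.1.6) and control risk 0.25 (section 1.2).

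**Formula** (two proportions, pooled z test), with p̄ the mean of p1 and p2:

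power = Φ[(|p1 − p2| − 1.96·s0) / s1], where s0 = √(2p̄(1 − p̄)/n) and s1 = √((p1(1 − p1) + p2(1 − p2))/n).

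**Step 1. Reproduce the printed figures.** Multiply 20% by the ratio instead of dividing. For 2.30: p1 = 0.20, p2 = 0.46, difference 0.26, s0 = 0.0940, s1 = 0.0904. Then (0.26 − 1.96 × 0.0940)/0.0904 = 0.837, and power = 79.9%.

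| Ratio | Pair | Power, n = 50 | Printed | Solved ratio for printed power |
|---|---|---|---|---|
| 2.30 | 20% vs 46.0% | 79.9% | 80% | 2.302 |
| 2.52 | 20% vs 50.4% | 90.1% | 90% | 2.516 |
| 3.00 | 20% vs 60.0% | 99.0% | 99% | 3.001 |

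All three rows match to two decimals. With n = 60 the solved ratios would be 2.18, 2.38 and 2.83; with 25% and n = 50 they would be 2.08, 2.25 and 2.63. So the table rests on 20% and 50, with 20% as the lower of the two risks.

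**Step 2. Compute what the column heading describes.** Divide 20% by the ratio. For 2.30: p2 = 0.20/2.30 = 0.0870, difference 0.1130, s0 = 0.0701, s1 = 0.0692. Then (0.1130 − 1.96 × 0.0701)/0.0692 = −0.352, and power = 36.2%.

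| Control risk, n per arm | Test | 2.30 | 2.52 | 3.00 |
|---|---|---|---|---|
| *Printed* | *not named* | *80%* | *90%* | *99%* |
| 20%, 50 | pooled z | 36% | 41% | 50% |
| 20%, 50 | chi-square, exact binomial power | 38% | 44% | 53% |
| 20%, 50 | Fisher | 26% | 30% | 38% |
| 20%, 60 | pooled z | 42% | 48% | 58% |
| 20%, 60 | chi-square, exact binomial power | 42% | 48% | 58% |
| 20%, 60 | Fisher | 33% | 38% | 48% |
| 25%, 60 | pooled z | 52% | 59% | 69% |
| 25%, 60 | chi-square, exact binomial power | 53% | 59% | 70% |
| 25%, 60 | Fisher | 43% | 50% | 62% |

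Other methods at 20% and 50 per group do not close the gap either: one-sided 49/54/63%, unpooled variance 37/42/52%, arcsine 38/43/53%, ratio read as an odds ratio 30/34/43%.

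**Step 3. What the design can detect.** With exact binomial power at 60 per arm, 80% power needs a ratio of about 4.8 (chi-square) or 6.7 (Fisher) from 20%, and about 3.7 or 4.4 from 25%. The printed value is 2.30.

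**Step 4. Precision.** At 60 per arm, an observed 20% vs 8.7% is a difference of 11.3 points. The 95% half-width is 1.96 × √((0.20 × 0.80 + 0.087 × 0.913)/60) = 12.4 points, so the interval includes zero.

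**The case against.** The strongest points on the other side, and what stands of each:

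- **It is a pilot.** The 120 comes from expected availability, no interim look or stopping rule uses the table, and the confidence interval planned in section 8.1.2 would itself show the imprecision. This is true and limits the harm to interpretation and later planning. It does not make the printed powers correct.
- **More favourable inputs can be built.** Section 1.2 gives 24.7% in-hospital mortality and 5.1% non-fatal recurrence in survivors, which combine to 0.247 + 0.753 × 0.051 = 28.5%. Section 4.2.2 allows up to 125 randomised, about 62 per arm. Together these give 61%, 67% and 78% by pooled z. That is above the 25%/60 figures but still well short of 80%, 90% and 99%.
- **Missing more often than not depends on 20%.** Correct. At 25% and 60 per arm, power for a ratio of 2.30 is 52 to 53% by z or chi-square and 43% by Fisher.
- **The recomputed values are not power for the planned analysis.** This stands as a caution. The 20% refers to fatal or recurrent stroke, while the composite adds TIA (sections 3.2 and 8.1.2) or new hemorrhagic stroke (section 7.1). The planned model is a logistic regression over six subgroups. The figures here keep to the endpoint and two-group comparison that section 8.1.5 itself uses.
- **The 50 may be evaluable patients, and both risks are approximate.** Possible, but no passage says so, and neither difference explains the table.

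**Conclusion.** The table is wrong as labelled. For a reduction from 20% with 50 per group, power is about 36%, 41% and 50% by the pooled z test (26% to 38% for the first row across Fisher and chi-square), which is 44 to 49 points below the printed values. At the planned 60 per arm it is about 42%, 48% and 58%.

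The printed values hold only for 20% against 46% to 60%. If 20% is the control risk, apixaban would be raising risk, contrary to the hypothesis in section 3.1. If 20% is the apixaban risk, the control risk would be 46% to 60%, contrary to both section 8.1.5 and section 1.2. The likely slip is that 20% was multiplied rather than divided by the ratio, or was entered for the wrong arm; the documents do not show which.

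The conclusion rests on the section's own inputs and an unadjusted comparison of two proportions. Exact percentages depend on the test, but no standard two-proportion test recovers the table. This should be corrected before the power statement is relied on.

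**What to change.** Replace the table in section 8.1.5 with power for a reduction from the stated control risk at 60 per arm, and name the test and the endpoint. For fatal or recurrent stroke and an unadjusted pooled z test, the printed ratios give about 42%, 48% and 58% from 20%, or 52%, 59% and 69% from 25%. Say that these are not power for the six-subgroup logistic model in section 8.1.2. If detectable ratios are kept, compute them with an exact method for the named test, because the normal approximation is unreliable near zero events.

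In the same edit:

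- reconcile 50 with 60 per group, or state what loss the 50 allows for;
- reconcile the 20% in section 8.1.5 with the 25% in section 1.2, or show both;
- add one line giving the expected half-width of the 95% confidence interval planned in section 8.1.2, about 12 points at 60 per arm for 20% vs 8.7%.

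The cost is protocol wording. Sample size, conduct and analysis do not change. The one downside is that the stated power will look less favourable.

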### 8.1.6 Randomization

Randomization of treatment was calculated in SAS 9.4 using a stratified, blocked PLAN procedure. For the 120 subjects to be randomized to either apixaban or warfarin, a random seed number was generated. Each subgroup of stroke type (small stroke, medium stroke and TIA) was randomized implementing block randomization using four blocks of 10. The treatment allocation was created by an unblinded statistician and given to the TGH research pharmacy. Blinded study envelopes are provided to study team members for randomization.

## 8.2 Interim Analysis

Due the small size and brief duration of the study no interim analyses are planned.

## 9 STUDY MEDICATION

**Apixaban** is a white to pale-yellow powder. At physiological pH (1.2–6.8), apixaban does not ionize; its aqueous solubility across the physiological pH range is ~0.04 mg/mL.

**Crystalline warfarin sodium** occurs as a white, odorless, crystalline powder that is discolored by light. It is very soluble in water, freely soluble in alcohol, and very slightly soluble in chloroform and ether.

### 9.1 Packaging

#### 9.1.1 Warfarin

Will be purchased by the Principal Investigator in and packaging will be based on manufacturer.

#### 9.1.2 Apixaban

Formulation and packaging details are below:

Product Description and Dosage Form	Potency	Primary Packaging (Volume)/ Label Type	Appearance	Storage Conditions (per label)
Apixaban Tablet	2.5 mg	Bottles of 60/ Marketed label	yellow, round, biconvex, film-coated tablets with “893” debossed on one side and “2½” on the other side.	Store at 20°C to 25°C (68°F-77°F); excursions permitted between 15°C and 30°C (59°F-86°F)

Apixaban Tablet	5 mg	Bottles of 60/ Marketed label	pink, oval-shaped, biconvex, film-coated tablets with “894” debossed on one side and “5” on the other side.	Store at 20°C to 25°C (68°F-77°F); excursions permitted between 15°C and 30°C (59°F-86°F)
--------------------	------	----------------------------------	--	--

## 9.2 Labeling

Apixaban and Warfarin bottles will be labeled by the PI with subject number, visit number at which they are to be dispensed, the medication name, pill strength and directions detailing dosing for study subjects.

## 9.3 Dosing

### 9.3.1 Warfarin

Warfarin will be dosed per the Dosage protocol found in appendix 13.4.

### 9.3.2 Apixaban.

The dosage of Apixaban is based on the clinical findings of studies in human subjects and its FDA approved dosage for patients with non-valvular atrial fibrillation. Patients will receive 5mg dosage twice a day or 2.5 mg if they have any 2 of the following characteristics:

- age  $\geq 80$  years
- body weight  $\leq 60$  kg
- serum creatinine  $\geq 1.5$  mg/dL

Coadministration with CYP3A4 and P- glycoprotein inhibitors: For patients receiving Apixaban 5 mg twice daily when Apixaban is coadministered with drugs that are strong dual inhibitors of cytochrome P450 3A4 (CYP3A4) and P-glycoprotein (P-gp) (e.g., ketoconazole, itraconazole, ritonavir, clarithromycin), the recommended dose is 2.5 mg twice daily [ patients already taking 2.5 mg twice daily, coadministration of Apixaban with strongdual inhibitors of CYP3A4 and P- glycoprotein should be avoided

If a dose of Apixaban is not taken at the scheduled time, the dose should be taken as soon as possible on the same day and twice-daily administration should be resumed. The dose should not be doubled to make up for a missed dose.

## 9.4 Treatment Compliance and Adherence

Subjects will be instructed to return all medication bottles (empty or partially used) at each study visit. The number of pills used will be counted and compared to the expected use to track treatment compliance.

Study medication will be counted to assess compliance at each clinic visit starting at day 14. Subjects who take between 75% and 125% of the prescribed dose will be considered compliant. Subjects who fall outside this range will be counseled and re-instructed on dosing procedures. Dose modifications along with the reasons for the modifications will be recorded on the CRF for each visit.

## 9.5 Drug Accountability

Records of study drug receipt and disposition will be maintained by the study sites including records of receipts, investigational drug orders, dispensing records, and disposition forms. These records will

be used to ensure that the investigational drug will not be distributed to any person who is not a study subject under the terms and conditions set forth in this protocol. The study medication is to be prescribed by the Investigator or designee and may not be used for any purpose other than that described in this protocol.

## 10 SAFETY MANAGEMENT

### 10.1 Clinical Adverse Events

Clinical adverse events (AEs) will be monitored throughout the study.

### 10.2 Adverse Event Reporting

All AEs that occur will be reported to the IRB. All SAEs will be reported to the IRB in accordance with IRB policies. AEs that are not serious will be summarized in narrative or other format and submitted to the IRB at the time of continuing review.

### 10.3 Definition of an Adverse Event

#### An Adverse Event

[AE] is defined as any new untoward medical occurrence or worsening of a pre existing medical condition in a patient or clinical investigation subject administered an investigational (medicinal) product and that does not necessarily have a causal relationship with this treatment. An AE can therefore be any unfavorable and unintended sign (including an abnormal laboratory finding, for example), symptom, or disease temporally associated with the use of investigational product, whether or not considered related to the investigational product.

- The causal relationship to study drug is determined by a physician and should be used to assess
- all adverse events (AEs). The causal relationship can be one of the following:
  - **Related:** There is a reasonable causal relationship between study drug administration and the AE.
  - **Not Related:** There is not a reasonable causal relationship between study drug administration and the AE.
- The term “reasonable causal relationship” means there is evidence to suggest a causal relationship.
- Adverse events can be spontaneously reported or elicited during open-ended questioning, examination, or evaluation of a subject. (In order to prevent reporting bias, subjects should not be questioned regarding the specific occurrence of one or more adverse events).

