### 2.3.2 Stroke/TIA Subtype Classification

#### 2.3.2.1 Ischemic Stroke

Defined as an acute symptomatic focal cerebral or retinal dysfunction caused by an infarction of central nervous system tissue.

1. a. Acute infarcts are classified as small, medium or large based on size of the largest ischemic lesion:
  - a. small = lesion in the anterior or posterior circulation <1.5 cm.
  - b. medium = equal to or greater than 1.5cm but less than a complete territory infarct lesion in a cortical superficial branch of the anterior cerebral artery (ACA), middle cerebral artery (MCA), posterior cerebral artery (PCA), or in a branch of MCA or PCA, or lesion in internal border-zone territories.
  - c. large posterior = lesion involving complete PCA territory, or lesion of cerebellum 1.5 cm or larger or any lesion of the brain stem.

- d. large anterior = lesion involving complete ACA or MCA territory, or lesion involving >1 artery territory
  - e. All classifications are based of the measurement of the largest lesion size with preferred sequencing to be GRE on MRI (*but all effort should be used to maintain the same modality of sequencing and magnet strength used at baseline*)
- 2.Subacute/chronic or 'old' infarcts (i.e. more than 2 weeks) are noted but not classified.
- 3.Transient Ischemic Attack (TIA)  
defined as an acute symptomatic focal cerebral, spinal, or retinal dysfunction in which symptoms resolve (typically in less than 1 day) without acute damage on neuroimaging.

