#### **3.2 Primary Objective**

In patients with atrial fibrillation with recent cerebral ischemic symptoms (0-48 hours), to evaluate whether the treatment regimen with Apixaban (Three subgroups: TIA: day 0-3; small stroke: day 3-5; medium stroke: day 7-9) compared with standard of care treatment regimen with warfarin (Three subgroups: TIA: day 7±5; Small or medium stroke: day 14±5) reduces the composite endpoint of fatal stroke, recurrent ischemic stroke or TIA at 30 and 180 days. (See figure 1)

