### **7 STUDY ENDPOINTS AND EVALUATIONS**

#### **7.1 Primary Endpoint**

Endpoint data will start at randomization up to 180 days. These composite endpoints include:

- Fatal stroke
- Recurrent Ischemic stroke
- New hemorrhagic stroke

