##### *Assessment Definition*

1 = Mild: Discomfort noted, but no disruption of normal daily activities; slightly bothersome; relieved with or without symptomatic treatment

2 = Moderate: Discomfort sufficient to reduce or affect normal daily activity to some degree; bothersome; interferes with activities, only partially relieved with symptomatic treatment

3 = Severe: Discomfort sufficient to reduce or affect normal daily activity considerably; prevents regular activities; not relieved with symptomatic treatment

For each solicited symptom, the subject will be asked if they sought medical advice (i.e. contact with a member of medical personnel) for this symptom.

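### Resolved TIA, a primary component in 3.2 and 8.1.2, depends mainly on history, yet the plan provides only non-targeted inquiry, and non-serious events are collected from a generally later day under warfarin

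*Combined protocol and SAP*

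**What the plan says.** **Endpoint.** Section 3.2 asks whether early apixaban "reduces the composite endpoint of fatal stroke, recurrent ischemic stroke or TIA at 30 and 180 days". Section 8.1.2 analyses the same three components: "fatal stroke, recurrent ischemic stroke, transient ischemic attack". Section 7.1, the endpoint section, has no TIA; its third component is "New hemorrhagic stroke".

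**Definition.** Section 2.3.2.1 defines TIA as a dysfunction "in which symptoms resolve (typically in less than 1 day) without acute damage on neuroimaging".

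**Inquiry.** Section 10.3 states: "Adverse events can be spontaneously reported or elicited during open-ended questioning, examination, or evaluation of a subject". It then adds: "In order to prevent reporting bias, subjects should not be questioned regarding the specific occurrence of one or more adverse events". The severity text in 10.4.2 points the other way: "For each solicited symptom, the subject will be asked if they sought medical advice". No list of solicited symptoms appears anywhere. Drug initiation (6.3), the treatment visits (6.4), end of study (6.5) and early withdrawal (6.6) each list a generic AE/SAE assessment and a review of concomitant medication changes (with procedures from 6.4 on). None lists a question about interval stroke, TIA or bleeding symptoms.

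**Start of collection.** Endpoints count from randomization (7.1). Non-serious AE collection begins at initiation of study drug (10.5.4). SAEs are collected from consent (10.4.1), but an emergency visit under 24 hours without admission is not an SAE unless it is judged life-threatening or an important medical event (10.4).

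**Masking.** The trial is open label (4.1), and the stroke adjudication committee knows the treatment arm (2.3).

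**The concern.** An open-ended rule suits general adverse events. Here it is also the only described way of asking about an efficacy endpoint that leaves nothing to find at the next visit. A coordinator following the plan as written would not ask whether the patient had passing weakness or speech trouble since the last contact. The committee can adjudicate only what reaches it, and no text says what triggers referral.

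Two things are at stake. Missed TIAs lower the event count in a trial of 120 patients. Pick-up may also differ between arms, because patients know their treatment, because the non-serious AE stream opens at different times, and because the number of contacts differs. The pilot is meant to supply data for larger studies (8.1.5), so a poorly ascertained TIA count would carry forward.

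**Working it through.** The plan gives no figure for TIA risk or pick-up, so there is nothing to reproduce. The check sets the passages side by side and then sizes the effect under stated assumptions.

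**1. What objective assessments can recover.** NIHSS, mRS and examination record status on the visit day. Follow-up MRI or CT is at day 14 and at end of study or early withdrawal (5.5), nominally 180 − 14 = 166 days apart. A TIA, as defined, leaves no deficit and no lesion for any of these to detect.

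**2. Length of the gaps.** Visits are at days 14, 30, 60, 90, 120, 150 and 180, so nominal gaps run from 14 to 30 days. With ±10-day windows the longest is (90 + 10) − (60 − 10) = 50 days.

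**3. Routes left.**
- Self-report, or open-ended questioning at the AE/SAE assessment.
- The medication/procedure review, if the TIA led to a work-up or a new drug.
- SAE reporting, if the patient was admitted or the event was otherwise judged serious.
- An unscheduled visit, which starts from the subject's own report (5.6.2).

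A brief TIA that led to no care can be found only by the first.

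**4. When non-serious collection opens, by arm (Table 2 windows).** Warfarin start minus apixaban start:
- TIA: day 2–12 versus 0–3. Window centres 7 − 1.5 = 5.5 days; extremes 2 − 3 = −1 to 12 − 0 = 12.
- Small stroke: day 9–19 versus 3–5. Centres 14 − 4 = 10 days; extremes 9 − 5 = 4 to 19 − 3 = 16.
- Medium stroke: day 9–19 versus 7–9. Centres 14 − 8 = 6 days; extremes 9 − 9 = 0 to 19 − 7 = 12.

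A TIA seen in an emergency department and discharged before drug start can therefore fall outside both AE streams, generally for longer under warfarin. The day-14 visit (day 11–17) may precede warfarin start and lists an AE assessment, which closes part of the gap in practice, but 10.5.4 as written has not yet opened non-serious collection. In the other direction, warfarin patients have extra unscheduled INR visits (5.2, 5.6.1) at which a TIA may be mentioned.

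**5. Size.** Let s be the stroke risk (equal in both arms and fully captured), t the true TIA risk (equal in both arms), and c₁ and c₂ the TIA pick-up by arm. If TIAs and strokes occur in different patients, the apparent composite ratio under no true effect is (s + t·c₁)/(s + t·c₂).
- From the plan: s = 20% (8.1.5).
- Assumed: t = 5–10%, c₁ = 80%, c₂ = 60%.
- t = 5%: (20 + 4)/(20 + 3) = 1.04.
- t = 10%: (20 + 8)/(20 + 6) = 1.08.
- With the 25% risk in section 1.2 instead: (25 + 4)/(25 + 3) = 1.04 and (25 + 8)/(25 + 6) = 1.06.

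If the arm with lower pick-up is the other one, the 20% results invert to 23/24 = 0.96 and 26/28 = 0.93. In patients, with 60 per arm, the spurious difference is 60 × 0.05 × 0.20 = 0.6 to 60 × 0.10 × 0.20 = 1.2. TIAs missed in total are 60 × 0.05 × (0.20 + 0.40) = 1.8 of 6, up to 60 × 0.10 × 0.60 = 3.6 of 12.

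**The case against.** **10.3 is a safety rule.** It sits under Safety Management and does not expressly forbid a separate endpoint questionnaire. The case report forms are not in the documents and might prompt for endpoints. The SS-QOL already asks about speech and vision at day 30 and end of study. This stands to the extent that the plan omits a targeted inquiry rather than banning one. But a recurrent TIA after dosing is an adverse event under 10.3, and the AE/SAE assessment is the only event inquiry the visit lists contain. The SS-QOL items ask about difficulty, not about a new episode.

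**Other routes exist.** The medication/procedure review can surface a work-up, SAEs are collected from consent, and doubtful cases call for an SAE report (10.4.1). This also stands, mainly for TIAs that led to medical care.

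**Most endpoints have objective checks.** Stroke with residual deficit is examined by NIHSS and mRS at each scheduled visit. Intracranial bleeding is assessed by MRI/CT. Major bleeding has haemoglobin and transfusion criteria, with laboratory tests at days 30, 90 and 180. This stands and narrows the point to resolved TIA and, in part, overt bleeding between visits.

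**Targeted prompting has its own bias.** The stated purpose of the open-ended rule is to prevent reporting bias, and prompting for subjective symptoms in an open-label trial may inflate soft events. This stands as a limit on the remedy.

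**Conclusion.** The point holds in limited form. If 3.2 and 8.1.2 govern, a primary component that depends mainly on history has no targeted inquiry, and part of the general inquiry opens later in one arm. If 7.1 governs, TIA is not primary and the point loses most of its weight for the primary analysis, so the three sections must be reconciled.

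The likely size is modest: a composite ratio of about 1.04–1.08 under no true effect. This rests on assumed TIA risks of 5–10% and pick-up of 60% versus 80%, neither of which is in the documents, and on the plan's 20% stroke risk in both arms.

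Three stronger readings are tempting and unsupported:
- A reader might infer that TIA rests wholly on unprompted reports. Section 10.3 allows open-ended questioning, examination and evaluation, so the accurate description is non-targeted inquiry.
- A reader might take 0.80/0.60 = 1.33 as the distortion. That ratio applies to TIA alone, not to the composite.
- A reader might infer a bias favouring one arm. Later AE collection under warfarin and extra INR contacts under warfarin oppose each other, and the documents do not show which dominates.

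**What to change.** - Reconcile 3.2, 7.1 and 8.1.2 on whether TIA is a primary component.
- State in 10.3 that the open-ended rule does not apply to primary and secondary endpoints.
- From randomization, use one short scripted checklist, identical in both arms, on new focal neurological symptoms (including resolved ones), emergency visits or head imaging since last contact, and bleeding.
- Give it at drug initiation (6.3), at every scheduled visit and early withdrawal (6.4–6.6), and at the monthly and day-210 calls. Each checklist should cover the whole interval since the last scheduled contact, so that extra INR visits do not create unequal ascertainment.
- Send every positive neurological answer to the adjudication committee.
- Delete or define the solicited-symptom sentence in 10.4.2.

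The cost is a one-page form, a few minutes per contact and more minor symptoms to adjudicate. The checklist reduces missed events. It does not remove bias from patients who know their arm or from a committee that knows it too.
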